4.5.1 Subject Replacement Strategy

Subjects who fail to complete study therapy before the first response assessment for reasons other than disease progression, death, SAE, or drug-related adverse events will be replaced, to allow response assessment in accordance with study stopping rules.

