3.1.7.1 Efficacy Endpoints

The primary endpoint is overall response rate assessed independently for each arm: relapsed/refractory FL (Arms A and C), and relapsed/refractory DLBCL (Arm B). Overall response rate is defined as the rate of complete + partial responses using CT criteria (Lugano 2014).²⁸

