4.3.2 Prohibited Concomitant Medications

Subjects are prohibited from receiving the following therapies during the Screening and Treatment Phase (including retreatment for post-complete response relapse) of this trial:

- Antineoplastic systemic chemotherapy or biological therapy
- Immunotherapy not specified in this protocol
- Chemotherapy not specified in this protocol
- Investigational agents other than pembrolizumab
- Radiation therapy

- Note: Radiation therapy to a symptomatic solitary lesion or to the brain may be allowed at the investigator's discretion.
- Live vaccines within 30 days prior to the first dose of trial treatment and while participating in the trial. Examples of live vaccines include, but are not limited to, the following: measles, mumps, rubella, varicella/zoster, yellow fever, rabies, BCG, and typhoid vaccine.
- Systemic glucocorticoids for any purpose other than management of rituximab-related hypersensitivity/infusion reactions; to modulate symptoms from an event of clinical interest of suspected immunologic etiology, or as physiologic corticosteroid replacement therapy for adrenal or pituitary insufficiency.

Subjects who, in the assessment by the investigator, require the use of any of the aforementioned treatments for clinical management should be removed from the trial. Subjects may receive other medications that the investigator deems to be medically necessary.

The Exclusion Criteria describes other medications which are prohibited in this trial.

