4.5 Subject Withdrawal/Discontinuation Criteria

Subjects may withdraw consent at any time for any reason or be discontinued from the trial at the discretion of the investigator should any untoward effect occur. In addition, a subject may be withdrawn by the investigator if enrollment into the trial is inappropriate, the trial plan is violated, or for administrative and/or other safety reasons. Specific details regarding discontinuation or withdrawal are provided in Section 6.1.3.1.

A subject must be discontinued from the trial for any of the following reasons:

- The subject or legal representative (such as a parent or legal guardian) withdraws consent.
- Confirmed radiographic disease progression

Note: For unconfirmed radiographic disease progression, patients may remain on study until progression is confirmed by repeat imaging or biopsy.

- Unacceptable adverse experiences as described in Section 6.2
- Intercurrent illness that prevents further administration of treatment
- Investigator's decision to withdraw the subject
- The subject has a confirmed positive serum pregnancy test
- Noncompliance with trial treatment or procedure requirements
- The subject is lost to follow-up
- Completed trial therapy, including Retreatment if applicable (see section 6.1.4.2, Treatment Period)
- Administrative reasons

Study visits are listed in Section 5 (Trial Flow Chart) and Section 6.1.4 (Visit Requirements). After the last cycle of pembrolizumab, each subject will be followed for 90 days for adverse event monitoring and will have an Off-Study visit at that time. Patients who discontinue for reasons other than progressive disease will have post-treatment follow-up as per standard of care, including disease status and survival.

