2. See Section 6.1.2.5: Baseline CT imaging must be performed within 8 weeks of initiating study drug therapy. CT neck should be included for patients with palpable or known neck adenopathy. End of induction CT will be done before cycle 5 (week 11-13 of therapy). For patients on continued therapy, restaging CT will be performed before cycle 9 (week 23-25) and then every 3 months thereafter. Other imaging may be performed at clinician's discretion, including FDG PET/CT and/or MRI.								
3. The presence of archival tissue will be assessed during screening. When available this tissue will be provided for central biomarker analysis including PD1/PDL1 expression on tumor cells. Patients may undergo optional lymph node biopsy at baseline and up to one time between cycles 1 and 3. Patients may also undergo optional biopsies in the setting of persistent or progressive disease, and tissue may be provided for correlative analysis at that time.								
4. See section 6.1.2.6 for details on correlative study draws, which are drawn at baseline (any time prior to cycle 1 day 1 study drug dosing), cycle 5 day 1, and at the Off-Study visit (or at the time of disease progression/initiation of second-line therapy whichever occurs first).								

5. Bone marrow aspirate (biopsy is not mandatory but is permitted) for routine analysis for lymphoma involvement will be performed at baseline for patients who have not undergone a marrow within 6 months prior to signing consent, and again to confirm complete response.

6. Negative Urine or serum pregnancy test is required within 72 hours prior to receiving the first dose of study medication.

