6.5 Reporting Requirements for Adverse Events/Adverse Reactions

6.6 Serious Adverse Events

A serious adverse event is any adverse event occurring at any dose or during any use of Merck's product that:

- Results in death;
- Is life threatening;
- Results in persistent or significant disability/incapacity;
- Results in or prolongs an existing inpatient hospitalization;
- Is a congenital anomaly/birth defect;
- Is a new cancer (that is not a condition of the study);
- Is associated with an overdose;
- Is another important medical event

Exceptions to Serious Adverse Event Reporting include events related to progression of the cancer under study, including hospitalization or death. These events are not to be reported as serious adverse events. Hospitalization related to convenience (e.g. transportation issues, etc.) will not be considered an SAE. Any serious adverse event, or follow up to a serious adverse event, including death due to any cause other than progression of the cancer under study that occurs to any subject from the time the consent is signed through 90 days following cessation of treatment, or the initiation of new anti-cancer therapy, whichever is earlier, whether or not related to Merck product, must be reported within 2 business days of investigator knowledge to Merck Global Safety.

Additionally, any serious adverse event, considered by an investigator who is a qualified physician to be related to Merck product that is brought to the attention of the investigator at any time outside of the time period specified in the previous paragraph also must be reported immediately to Merck.

SAE reports and any other relevant safety information are to be forwarded to the Merck Global Safety [contact]

A copy of all 15 Day Reports and Annual Progress Reports is submitted as required by FDA, European Union (EU), Pharmaceutical and Medical Devices agency (PMDA) or other local regulators. Investigators will cross reference this submission according to local regulations to the Merck Investigational Compound Number (IND, CSA, etc.) at the time of submission. Additionally investigators will submit a copy of these reports to Merck & Co., Inc. (Attn: Worldwide Product Safety; [contact]) at the time of submission to FDA.

All subjects with serious adverse events must be followed up for outcome.

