7.0 STATISTICAL ANALYSIS PLAN

This study administers therapy to two groups of patients, relapsed/refractory FL and relapsed/refractory DLBCL.

Subjects who fail to complete study therapy or withdraw consent before the first response assessment for reasons other than disease progression, death, SAE, or drug-related adverse events will be replaced, to allow response assessment in accordance with study stopping rules. The first group (Arm A) includes patients with relapsed or refractory follicular lymphoma, and will include at least 9 patients with rituximab-refractory disease.

The second group (Arm B) consists of patients with relapsed/refractory diffuse large B-cell lymphoma ineligible for, or failing to respond to or progressing, after autologous stem cell transplantation.

These groups will employ independent rules, using Simon's two-stage design, and accrual will be suspended for review if futility thresholds are met. Two-stage designs which limit the maximum sample size will be considered. Once enrollment is suspended, the nature of events to leading to stopping will be assessed by the Principal Investigator and reported to institutional regulatory authorities, in accordance with the institutional Data Safety Monitoring Plan. The institutional Data Safety Monitoring Committee will determine whether any further accrual may proceed. Statistical analysis will entail descriptive statistics. Categorical variables will be summarized by number and percentage, and continuous variables will be summarized by min/median/max/mean/sd, respectively. Overall response rate, and response quality, will be evaluated according to CT criteria and PET/CT in relevant patients, as per the 2014 Lugano criteria.²⁸ PFS/OS distribution will be estimated and Kaplan-Meier curves will be presented. Log-rank testing and Cox proportional hazard regression models might be applied to evaluate the association between survival endpoints and prognostic factors. To compare continuous variable in the correlative studies, student's t-test and regression analysis might be applied if deemed appropriate.

Subjects who fail to complete study therapy before the first response assessment for reasons other than disease progression, death, SAE, or drug-related adverse events will be replaced, to allow response assessment in accordance with study stopping rules.

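### The replacement rule can take informative early exits out of the response denominator, and no all-treated response analysis is planned; type I error can then exceed the design value, most of all in Arm C.

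*Combined protocol and SAP*

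**What the plan says.** Under section 4.5.1, patients who stop before the first response assessment "for reasons other than disease progression, death, SAE, or drug-related adverse events will be replaced, to allow response assessment". Section 7.0 states the rule twice, once in a wider form that begins "Subjects who fail to complete study therapy or withdraw consent before the first response assessment", with the same four exceptions.

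Four other places bear on how the rule works:

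- Section 4.3.2 says that patients who, in the investigator's view, "require the use of any of the aforementioned treatments for clinical management should be removed from the trial". Needing prohibited therapy is not itself one of the four exceptions.
- Section 4.5 gives "Confirmed radiographic disease progression" as its only progression-based reason for discontinuation. It also lists withdrawn consent, investigator decision, noncompliance, loss to follow-up and administrative reasons.
- Section 6.6 exempts from SAE reporting "events related to progression of the cancer under study, including hospitalization or death".
- Note 2 to the flow chart (section 5.1) places the first planned restaging CT before cycle 5, at week 11-13.

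On the endpoint, section 3.1.7.1 says "Overall response rate is defined as the rate of complete + partial responses using CT criteria". No section defines the ORR analysis set or says how a replaced patient is scored.

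**The concern.** About three months pass between the first dose and the first planned scan. A patient whose lymphoma worsens in that time may withdraw, be taken off by the investigator, or need therapy that the protocol prohibits. Whether that patient counts depends on the recorded reason. If it is progression, the patient is kept; if it is consent withdrawal or investigator decision, the patient is replaced. The SAE exception does not reliably close the gap, because hospitalization for worsening lymphoma is not reported as an SAE. The trial is open-label and single-center, with scans read locally, so the coding is done by people who know how the arm is going.

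If such exits are more often failures than the rest and drop out of the count, the observed ORR is too high. An inactive regimen then has a better chance of passing the Simon rule than section 7.1 states.

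**Working it through.** **1. Reproduce the design figures.** Inputs are from sections 7.1.1 to 7.1.3. With stage 1 size n1, stop if r1 or fewer respond, total n, and reject if r or more respond, the probability of rejection at true rate p is

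R(p) = sum over x = r1+1 to n1 of P(Bin(n1, p) = x) × P(Bin(n − n1, p) ≥ r − x).

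| Arm | n1, r1 | n, r | p0 | p1 | Stated alpha / power | Exact alpha / power |
|---|---|---|---|---|---|---|
| A | 7, 2 | 20, 10 | 0.30 | 0.60 | .05 / 0.82 | 0.041 / 0.82 |
| B | 9, 2 | 17, 7 | 0.20 | 0.50 | .05 / .8 | 0.034 / 0.81 |
| C | 12, 5 | 25, 16 | 0.45 | 0.70 | .04 / 0.80 | 0.043 / 0.80 |

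Power reproduces in all arms. Alpha matches at the printed precision only in C. In A and B the stated .05 lies above the exact value and reads as a nominal ceiling.

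**2. Model replacement.** Let d be the share of treated patients replaced, f the rate at which they would have responded, and q the rate among those kept. If p0 is the rate in all treated patients, p0 = (1 − d)q + d·f. Hence:

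- all replaced are failures (f = 0): q = p0/(1 − d)
- half the null rate (f = p0/2): q = p0(1 − d/2)/(1 − d)
- like the rest (f = p0): q = p0, so alpha does not change

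The documents give no value for d or f; both are assumptions. Example, Arm C, d = 10%, f = 0: q = 0.45/0.90 = 0.50, and R(0.50) = 0.112.

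| Arm | Exact design alpha | d = 5%, all failures | d = 5%, half rate | d = 10%, all failures | d = 10%, half rate |
|---|---|---|---|---|---|
| A | 0.041 | 0.057 | 0.049 | 0.079 | 0.058 |
| B | 0.034 | 0.044 | 0.039 | 0.057 | 0.045 |
| C | 0.043 | 0.070 | 0.055 | 0.112 | 0.071 |

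**3. Scale.** One replaced failure in a fully accrued arm is 1/21 = 4.8% (A), 1/18 = 5.6% (B) or 1/26 = 3.8% (C) of treated patients. Setting q = p0(n + 1)/n gives alpha of 0.056, 0.045 and 0.062. The 5% scenario is therefore about one patient per arm. With all replaced patients failures, alpha passes 0.05 at d of about 3% (A), 7.5% (B) and 1.6% (C).

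**4. Power.** By the same mechanism at the alternative, with d = 10% and f = 0, R(p1/(1 − d)) = 0.93, 0.90 and 0.96. Replacement raises power.

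**The case against.** Several parts of the case against the concern stand.

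- A reader might infer that every patient who worsens clinically is replaced. The text does not say so. *Disease progression* is an unqualified exception in 4.5.1 and 7.0, and it can cover a patient who withdraws, or needs chemotherapy, because the lymphoma is growing. Set beside section 4.5, this is an ambiguity, not a stated exclusion. Withdrawn consent and prohibited therapy for reasons outside the four exceptions do lead to replacement.
- A reader might infer a planned exclusion from ORR. Removal from the denominator is itself an inference. It rests on the word *replaced*, on the stated purpose of allowing response assessment, and on decision rules and enrollment caps both set at 20, 17 and 25. The demonstrable gap is that the analysis set is undefined.
- A reader might infer that both Simon error rates are understated. Only type I error can be; type II error falls.
- A reader might infer that every arm exceeds its stated alpha. Arm B stays below .05 at 5% even if all replaced patients are failures, and Arm A stays just below at 5% in the half-rate case.
- The exceptions already keep the most informative exits, and administrative reasons or loss to follow-up need not signal non-response. No figure in the documents shows that the remaining exits are enriched for failure.
- Sections 7.1.1 to 7.1.3 call p0 and p1 end-of-induction rates without naming the population. If p0 is a rate among assessed patients only, the inflation disappears.

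None of this supplies the missing analysis set or a definition of progression for the replacement rule.

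**Conclusion.** The concern holds in conditional form. The plan replaces some treated patients for reasons that may be linked to non-response, leaves the treatment of clinical worsening to coding, and plans no analysis that would show the effect. Any inflation of type I error rests on three assumptions: that replaced patients leave the denominator, that the null rate refers to all treated patients, and that replaced patients respond less often than the rest.

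Under those assumptions, one replaced failure per arm is enough to take Arms A and C above their stated levels, while Arm B has slack. Arm C is the most sensitive: it exceeds its stated .04 in all four scenarios tabulated, from 0.055 to 0.112. The plan should be changed, but the documents do not show that the trial's result will be wrong.

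**What to change.** 1. Report ORR in all treated patients beside the Simon result, counting every unassessed or replaced patient as a non-responder. Describe a rejection that does not hold there as not robust. One definite way to judge this is to apply the same thresholds to the first 20, 17 and 25 treated patients in order of enrollment.
2. In 4.5.1 and 7.0, state for the analysis that *disease progression* includes investigator-documented clinical progression and the start of other anti-lymphoma therapy for worsening disease. State also that these patients, and those who withdraw consent after dosing, count as non-responders. Radiation to a lesion should not be scored as non-response on its own, because section 4.3.2 allows some radiation on study.

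This changes the scoring of exits only, not who is treated or removed. The cost is SAP wording and one table; no patients are added.

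The downside depends on what p1 means. If it applies only to assessed patients and 5% are unassessed, all-treated power is R(0.95·p1) = 0.75 (A), 0.75 (B) and 0.68 (C). If it applies to all treated patients, power stays at 0.82, 0.81 and 0.80. The alpha figures above take p0 as an all-treated rate, so the 0.75/0.75/0.68 figures rest on a different premise from theirs. The SAP should say which population p0 and p1 describe.

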4.6 Clinical Criteria for Early Trial Termination

Early trial termination will be the result of the criteria specified below:

- Quality or quantity of data recording is inaccurate or incomplete
- Poor adherence to protocol and regulatory requirements
- Incidence or severity of adverse drug reaction in this or other studies indicates a potential health hazard to subjects
- Plans to modify or discontinue the development of the study drug

In the event of Merck decision to no longer supply study drug, ample notification will be provided so that appropriate adjustments to subject treatment can be made.

5.0 TRIAL FLOW CHART

5.1 Study Flow Chart

Trial Period:	Screening Phase	Treatment – Induction (cycles 1-4)					Treatment – Extended therapy (cycles 5, up to 35 max)	Off-Study Visit
Treatment Cycle/Title:	Study Screening	Cycle 1 day 1	Cycle 1 day 8	Cycle 1 day 15	Cycle 2 day 1	Cycle 3-4 day 1	Cycles 5-35, day 1	90 days after last dose of pembrolizumab
Scheduling Window (Days):	-42 to -1	± 3	± 3	± 3	± 3	± 3	± 5	+/- 7
Administrative Procedures								
Informed Consent	Х							
Inclusion/Exclusion Criteria	Х							
Medical History	Х	\mathbf{X}^1			X	X	Х	Х
Prior and Concomitant Medication Review	Х	\mathbf{X}^1			X	X	Х	Х
Arm A & B: Rituximab Administration		Х	Х	X	Х			
Arm A, B & C: Pembrolizumab Administration		Х			X	X	Х	
Arm C: Obinutuzumab administration		Х	X	X	X		(Cycles 5,9,13,17,21,25 only)	
Post-study anticancer therapy status								Х

Survival Status								х
Clinical Procedures/Assessment	s				1	1	1	
Review Adverse Events	X (baseline AE)	\mathbf{X}^1			X	X	X	Х
Full Physical Examination	Х							Х
Directed Physical Examination		X^1			X	Х	Х	
Vital Signs and Weight (Height at Screening)	Х	\mathbf{X}^1			X	X	X	Х
ECOG Performance Status	Х	\mathbf{X}^1			x	X	x	Х
Laboratory Procedures/Assessm	ients: analysis perfo	ormed by L	OCAL	laborator	y	1		
Pregnancy Test – Urine or Serum β-HCG	X ⁶							
PT/INR and aPTT	Х							
CBC with Differential	Х	X^1			X	Х	Х	Х
Comprehensive Chemistry Panel, LDH	Х	\mathbf{X}^1			X	X	X	Х
Urinalysis	Х							
T3, FT4 and TSH	Х				X	Х	Х	Х
HepB S Ag, Hep B Core Ab, Hep C Ab	Х							
Efficacy Measurements								
Tumor Imaging	X ²						X- within 2 weeks before starting Cycle 5 and Cycle 9, then q 4 cycles (q 3 mo) ²	
Bone marrow aspirate	X ⁵							
Tumor Biopsies/Archival Tissue Collection/Correlative Studies Blood								
Archival or Newly Obtained	X ³	X ³	X ³	X ³	X ³			

Tissue Collection								
Correlative Studies Blood Collection	X ⁴						X ⁴	X4
1. Medical history, AE review, Prior/Concomitant medication review, weight, and ECOG, PE, height/weight, and lab studies do not need to be repeated if done within 7 days of start cycle 1 day 1 (e.g. at screening visit). VS should be recorded at screening and at each treatment visit.								
2. See Section 6.1.2.5: Baseline CT imaging must be performed within 8 weeks of initiating study drug therapy. CT neck should be included for patients with palpable or known neck adenopathy. End of induction CT will be done before cycle 5 (week 11-13 of therapy). For patients on continued therapy, restaging CT will be performed before cycle 9 (week 23-25) and then every 3 months thereafter. Other imaging may be performed at clinician's discretion, including FDG PET/CT and/or MRI.								
3. The presence of archival tissue will be assessed during screening. When available this tissue will be provided for central biomarker analysis including PD1/PDL1 expression on tumor cells. Patients may undergo optional lymph node biopsy at baseline and up to one time between cycles 1 and 3. Patients may also undergo optional biopsies in the setting of persistent or progressive disease, and tissue may be provided for correlative analysis at that time.								
4. See section 6.1.2.6 for details on correlative study draws, which are drawn at baseline (any time prior to cycle 1 day 1 study drug dosing), cycle 5 day 1, and at the Off-Study visit (or at the time of disease progression/initiation of second-line therapy whichever occurs first).								

5. Bone marrow aspirate (biopsy is not mandatory but is permitted) for routine analysis for lymphoma involvement will be performed at baseline for patients who have not undergone a marrow within 6 months prior to signing consent, and again to confirm complete response.

6. Negative Urine or serum pregnancy test is required within 72 hours prior to receiving the first dose of study medication.

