2.3 Exploratory Objectives

- (1) To explore correlates of response using peripheral blood flow cytometry.
- (2) To evaluate the PDL1/PD1 axis and tumor microenvironment, using biopsies performed at baseline, between cycles 1 and 3, and at the time of persistent/progressive disease (optional).
- (3) Explore treatment outcomes in subsets of enrolled patients with rituximab-refractory follicular lymphoma

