3.1.7.2 Biomarker Research

Tissue-based assays for tumor and immune infiltrate expression of PD1, PD-L1 will be performed by a third party laboratory to be designated by Merck, with tissue received from the most recent biopsy specimen when available.

Patients may undergo an optional tumor biopsy at baseline and up to one time between cycles 1 and 3. Patients may also undergo optional biopsies in the setting of persistent or relapsed disease. Correlative studies will evaluate the tumor microenvironment.

For all patients, baseline and serial evaluation of peripheral blood T cell populations by flow cytometry will be undertaken. In previous studies, alterations of both PD-L1 and PD1 bearing lymphocytes have been observed in peripheral blood. This study will analyze markers including (but not limited to) CD3, CD4, CD8, CD14, PD-1, PD-L1, and PDL-2 on peripheral blood mononuclear cells, and will explore whether alterations in T cell subsets occur with therapy and predict outcomes with treatment.

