6.1.2.6 Tumor Tissue Collection and Correlative Studies Blood Sampling

Assessment of available archival tumor tissue for correlative study analysis will be performed during the screening period. Any available pretreatment biopsy tissue will be provided for central correlative study analysis. In addition, patients will undergo optional lymph node biopsy at baseline and up to one time between cycles 1 and 3, and at the time of persistent or progressive disease. Correlative studies will evaluate the tumor immunomicroenvironment.

Peripheral blood correlative study samples will be performed at the following time-points (see Section 5 Trial Flow Chart):

- 1. Baseline (collected any time prior to cycle 1 day 1 study drug dosing)
- 2. Cycle 5 day 1

3. At the Off-Study assessment visit; or at the time of disease progression, or at time of initiation of second-line therapy (whichever occurs first)

Specimen Requirements: Submission for flow cytometry

- A 5-10 mL specimen of peripheral blood in lavender- (EDTA) or green- (sodium heparin) tube is acceptable for each draw.
- Storage/Transport Temperature: Specimens can be transported with a cold pack or wet ice, but do not fix or freeze specimens.
- Unacceptable Conditions: Frozen specimens, specimens greater than 48 hours old, specimens fixed in formalin for flow cytometry

• Address for shipping blood specimens for flow cytometry: Attn: Hematopathology Lead Seattle Cancer Care Alliance Hematopathology Laboratory G7800 [name]

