6.1.4.2 Treatment Period

The treatment period begins with the first administration of study treatment, and is designated as Cycle 1 Day 1.

- **6.1.5 Induction phase:** The induction phase will consist of four cycles lasting 3 weeks: pembrolizumab 200 mg on day 1 every 3 weeks, and rituximab (Arms A and B) or obinutuzumab (Arm C) on day 1 (after pembrolizumab) x 4 doses (Cycle 1 day 1, 8, 15, and cycle 2 day 1).
- **6.1.6 Extended Therapy Phase:** Patients with at least a partial response may continue on extended therapy: pembrolizumab 200 mg day 1 every 3 weeks for up to 2 years maximum of 35 infusions.) In addition, for arm C, patients with stable disease or better, who are experiencing clinical benefit in the judgment of the investigator, may receive up to 6 more doses of obinutuzumab every 3 months (cycles

5,9,13,17,21,and 25) in combination with pembrolizumab every 21 days, up to 35 cycles.

6.1.6.1 Discontinuation of Study Therapy after CR: Patients may elect to stop therapy during the extended therapy phase, if in CR after at least 8 cycles (24 weeks) of pembrolizumab therapy. CR may be defined by CT, PET-CT, either in conjunction with biopsy when applicable (including marrow assessment). These patients are eligible for the Second Course period as in section 6.1.6.2 if no cancer treatment was administered since the last dose of pembrolizumab, the subject meets the safety parameters listed in the Inclusion/Exclusion criteria, and the trial is open. Ninety days after receiving the last dose of pembrolizumab, subjects in CR who are potential retreatment candidates may convert to standard of care surveillance visits, while remainingeligible for the Second Course period as in 6.1.6.2.

6.1.6.2 Second Course (retreatment) Period:

Subjects who elect to stop study therapy for proven CR are eligible for up to one year of additional pembrolizumab therapy, and for Arm C patients q12 week obinutuzumab (maximum of 6 courses q 3 months, and 10 total doses, including all prior doses) if they progress after stopping study treatment.

This retreatment is termed the Second Course Phase of this study and is only available if the study remains open and the subject meets the following conditions:

• Stopped therapy after receiving at least 8 cycles (24 weeks), and attaining an investigator-determined CR (CT, PET-CT, and/or biopsy-proven CR).

AND

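### In Arms A and B, on-treatment change in blood T-cell subsets cannot be compared by response at a common time, because the only fixed draw is at cycle 5 day 1 and only patients with PR or better continue to cycle 5

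*Combined protocol and SAP*

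**What the plan says.** The first exploratory objective (section 2.3) is "To explore correlates of response using peripheral blood flow cytometry". Section 3.1.7.2 is more specific. It states "For all patients, baseline and serial evaluation of peripheral blood T cell populations by flow cytometry will be undertaken", and adds that the study "will explore whether alterations in T cell subsets occur with therapy and predict outcomes with treatment". The aim therefore covers change on therapy as well as pre-treatment status.

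Section 6.1.2.6 lists three draws:

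- "Baseline (collected any time prior to cycle 1 day 1 study drug dosing";
- cycle 5 day 1;
- "At the Off-Study assessment visit; or at the time of disease progression, or at time of initiation of second-line therapy (whichever occurs first".

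Note 4 to the flow chart (section 5.1) repeats this schedule, with the draws after baseline at "cycle 5 day 1, and at the Off-Study visit (or at the time of disease progression/initiation of second-line therapy whichever occurs first", and the chart marks no correlative draw in cycles 1 to 4.

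Entry to cycle 5 is governed by section 6.1.6: "Patients with at least a partial response may continue on extended therapy". Section 1.1 gives the same rule for Arms A and B. In Arm C, patients with stable disease and clinical benefit may also continue. The flow chart places tumor imaging "within 2 weeks before starting Cycle 5 and Cycle 9", so the response CT comes before the cycle 5 draw.

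Section 7.0 says only that a t-test and regression might be used for the correlative data. It names no time point and does not say how absent samples will be handled.

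**The concern.** In Arms A and B the one fixed on-treatment sample is conditional on response, which is the outcome it is meant to help explain. Patients with stable or progressive disease at the end of induction would not normally reach the visit where it is taken. Their second sample comes at a time set by what happens to them.

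A contrast of change from baseline using whatever second sample exists would mix response with sampling time, drug exposure and progression. Patients in two of the three arms would give serial blood that cannot answer the on-therapy part of the question in section 3.1.7.2.

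**Working it through.** The documents give no sample size, power or alpha for the correlative work, so there is no stated figure to reproduce. The check sets the sampling schedule against the continuation rule, first by day and then by number of patients.

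**Timing.** Cycles last 21 days, so day 1 of cycle k falls on day 21(k − 1) + 1.

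- Cycle 4 day 1: 21 × 3 + 1 = day 64.
- Cycle 5 day 1: 21 × 4 + 1 = day 85. The flow chart window of ±5 days gives days 80 to 90.
- End-of-induction CT, within the two weeks before cycle 5: days 85 − 14 = 71 to 84.
- Off-Study visit if the last pembrolizumab dose is at cycle 4 day 1: 64 + 90 = day 154. The ±7 day window gives days 147 to 161.

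**Second sample after baseline in Arms A and B, by end-of-induction result.**

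| Result | Next draw | Approximate day |
|---|---|---|
| PR or better, continuing | Cycle 5 day 1 | 85 |
| Progression on the CT | At progression | 71 to 84 |
| Stable disease, no later progression or new therapy | Off-Study visit | 154 |
| Stable disease, then progression or new therapy before Off-Study | At that event | Before 154 |

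For stable disease without a later event, the draw is 154 − 85 = 69 days after the responders' draw and 90 days after the last pembrolizumab dose.

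**Numbers at full accrual and the assumed response rates** (sections 7.1.1 and 7.1.2). Expected non-responders = n × (1 − ORR).

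- Arm A: 20 × (1 − 0.60) = 8.
- Arm B: 17 × (1 − 0.50) = 8.5.
- Together: 16.5 of 37.

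**Numbers at the null rates.** Full accrual would give 20 × 0.70 = 14 and 17 × 0.80 = 13.6. Those counts ignore the first-stage stop, so the expected sample size is needed.

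- Arm A: the probability of 2 or fewer responses in 7 at 30% is 0.647. Expected n = 7 + 13 × (1 − 0.647) = 11.6, and 11.6 × 0.70 is about 8 non-responders.
- Arm B: the probability of 2 or fewer responses in 9 at 20% is 0.738. Expected n = 9 + 8 × (1 − 0.738) = 11.1, and 11.1 × 0.80 is about 9 non-responders.

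Allowing for early stopping under the null, the expected number of patients without the sample is thus again about 8 and 9. It is then a larger share of a smaller arm.

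**The case against.** A reader might infer that blood correlates of response cannot be compared between responders and non-responders at all. The documents do not support that.

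- Baseline blood is drawn in every patient, and the objective in section 2.3 is not limited to change on treatment. Baseline markers can be compared by response in all three arms.
- Arm C is the largest arm (25 of 62 planned patients). Its patients with stable disease and clinical benefit go on to cycle 5, so some non-responders there have the sample.
- Patients with progression on the end-of-induction CT are drawn at about days 71 to 84, close to day 85. The long delay applies only to stable disease without an earlier event. The documents give no split between stable and progressive disease, so the size of that group is unknown.
- Section 4.5 lets patients with unconfirmed progression remain on study, so a few Arm A or B non-responders might still be sampled.

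Nor should the cycle 5 sample be read as having no predictive use. It follows the response CT in every arm, so it cannot prospectively predict end-of-induction response. Section 3.1.7.2 speaks of outcomes generally, however, and the sample can be a landmark for later PFS and OS among patients who continue. Sampling at the end of induction is also a reasonable way to describe whether T-cell subsets change with therapy.

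All of this stands and limits the point. It does not supply Arm A and B non-responders with a sample at a common on-treatment time. The draw at progression comes near the right day, but the outcome itself triggers it.

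**Conclusion.** The concern holds for one comparison: change from baseline at a common on-treatment time, responders against non-responders, in Arms A and B. At full accrual and the assumed response rates, about 8 of 20 and 8 to 9 of 17 patients would normally lack the sample, which leaves few or no non-responders at that time point. Their replacement sample falls anywhere from about day 71 to about day 154, depending on outcome.

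This assumes 21-day cycles without delay, a last dose at cycle 4 day 1 for patients who do not continue, and the PR-or-better rule applied as written.

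Baseline comparisons and the primary ORR analysis are not affected. The finding is not extended to Arm C, beyond the fact that its cycle 5 sample also follows the CT. Severity is minor: the objective is exploratory and no decision rule depends on it.

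**What to change.** In section 6.1.2.6 and flow chart note 4, replace the cycle 5 day 1 draw with one of these:

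- **Cycle 4 day 1 in all patients still on treatment.** This precedes both the end-of-induction CT and the selection on response at cycle 5. CBC and chemistry are already drawn at that visit.
- **End-of-induction restaging in every patient, whether or not cycle 5 is started.** This stays close to any cycle 5 samples already collected, but is not clearly ahead of the response assessment.

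Name the chosen time point in section 7.0 as the one for the responder contrast, and report the progression or Off-Study sample separately as description.

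The costs are small. Responders give the same number of samples, while Arm A and B non-responders give one more research tube. Patients who stop before the new draw are still missed, so their number should be reported. With the cycle 4 option, new samples are 85 − 64 = 21 days earlier than any already taken at cycle 5, so time point should be recorded and noted or adjusted for in the analysis. Treatment does not change.
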